#### **D. Research Population & Recruitment Methods**

**Procedure 1 (Intervention Study):** The participant population are fathers who are in recovery from substance use disorders and have been abstinent from illicit substances for less than 18 months. Participants must be over the age of 18 years old. Our primary intervention target is fathers with opioid use disorder and efforts will be made to prioritize fathers who have specifically misused opioids in the past.

Fathers are eligible to participate if:

1. They identify as being in recovery and have been abstinent from illicit substances for at least 1 day and less than 18 months.
2. They have parenting responsibilities for a child between the ages of 3-16 who they spend at least 2 hours per week with.
3. They speak English.
4. They are 18 and older.

The project coordinator will complete the eligibility screener via text message or phone call. Individuals will be asked to describe their recovery and family situation to the project coordinator through open ended questions. Individuals will be excluded if they do not meet eligibility criteria, or if they deny answering questions about their recovery and family situation. Individuals will be excluded if they cannot speak English because they will not be able to understand intervention content and will not be able to participate in surveys. Father's must have potential to have some contact following treatment since the intervention is targeted at improving parenting skills. Fathers of children younger than 3 or older than 16 will be excluded because the intervention is not suitable for children outside of the age range 3-16.

The total number of participants will not exceed 80 for procedure 1. Our goal is to recruit approximately 40 fathers to the intervention condition and 40 fathers to the control condition. This will provide enough data to compare effectiveness between condition and also to examine the effects of different substances on intervention outcomes. We expect these numbers may be less due to COVID-19.

The PI or a research assistant will recruit participants. If a research assistant recruits participants, they will be trained by the PI to use the **Text Message** script. See the Text Message document for screening procedures. Language and device access will not be specifically screened for, because participants would only be able to contact the study team if they read the delivered text which was in English and could respond to the questions we are asking. We believe asking this question would place an unnecessary burden on participants.

The individuals who will recruit participants have not and will not provide treatment or care to the prospective participants.

The clinician also has a role in intervention development. The clinician will not have access to the data to diminish undue influence.

There are no costs to the participant or third party.

Participants will receive \$25 for the baseline questionnaire, \$50 for the post questionnaire, and \$75 for the follow-up questionnaire. Participants in the intervention condition will also receive \$5 per knowledge quiz they complete (up to a total of \$30). Participants in the intervention condition will receive a certificate of completion indicating the number of video session completed (as indicated by the number of knowledge tests completed) and the number of coaching calls participated in. Participants will be given the choice to receive either a check in the mail or electronic gift card following each survey. Individuals participating in the intervention will receive a lump sum for all knowledge tests they completed at the end of the intervention and will similarly be given the choice to either receive an electronic gift card or check in the mail.

Participants will be texted after they complete the baseline survey and before they receive the Week 1 texts, "You have the opportunity to receive additional cash incentive: if you refer someone to the study who is

eligible to participate, you will receive an additional \$5 incentive. You can refer up to two people. Make sure to instruct the referred individual to provide your name when they take the survey in order to receive incentive. Importantly, you will only receive the \$5 incentive if the person you referred meets eligibility criteria. Feel free to contact the research team with questions or request for details regarding eligibility requirements, [contact]." (see "Text Messages" script). Participants will only receive the incentive payment(s) if the person(s) they refer is deemed eligible for participation.

Participants will have the opportunity to communicate if they were referred by someone within the baseline survey in Qualtrics. We will add a display logic question: "Did someone refer you to participate in this study?" If so, "What is the name of the person who referred you?" (see "Baseline\_referral questions.docx"). We will cross-check the identified name in our database to document referral and initiate reimbursement. Participants will have the opportunity to communicate how they heard about the research study within the baseline surveys in Qualtrics for Procedures 1 and 2. We will add a fill in the blank question, "how did you hear about this study?" to track how participants learned about the current study they are engaged in. In attempt to reduce bias: 1) each participant will be limited to two verified recommendations, 2) only the first 20 participants will be provided this option to refer someone to the study.

Participants are being incentivized more at the post and follow-up surveys to improve the likelihood of longitudinal data collection.

**Procedure 2 (Baseline Only Survey):** The participant population are fathers who are in recovery from substance use disorders and have been abstinent from illicit substances for less than 3 years (36 months). Participants must be over the age of 18 years old. Our primary intervention target is fathers with opioid use disorder and efforts will be made to prioritize fathers who have specifically misused opioids in the past.

Fathers are eligible to participate if:

1. They identify as being in recovery and have been abstinent from illicit substances for at least 1 day and less than 3 years (36 months).
2. They have parenting responsibilities for a child between the ages of 3-16 who they spend at least 2 hours per week with.
3. They speak English.
4. They are 18 and older.

The total number of participants will not exceed 120 for the baseline only survey. This number includes the participants who also participated in procedure 1 so we would recruit 120-number recruited for procedure 1. We anticipate that recruitment is finished for procedure 1 and we have enrolled only 41 subjects, thus, we expect that no more than 79 participants will be recruited for the baseline only survey.

Similar procedures for virtual recruitment from procedure 1 will be followed in the event of virtual recruitment for procedure 2. For procedure 2, the project team may travel to treatment centers to complete the eligibility screener and offer the chance to complete the survey in person via an iPad. Treatment centers will allow the research team to be present on site, and will provide an indoor or outdoor space that allow for sufficient spacing and privacy to mitigate risks associated with COVID-19 transmission and loss of privacy. The treatment centers will let fathers know that the study team is on site and fathers will voluntarily approach the study team in a location where the study team is not able to see treatment center attendees to mitigate HIPAA privacy concerns. We will work with treatment centers who consent to in-person recruitment to determine the best process to talk with clients while on site. This might vary based on the type of treatment center. For example, the Methadone clinic has people coming and going regularly, thus

the option to set up a booth might be an effective strategy to be visibly available to anyone walking through. Another example is that outpatient treatment centers might allow us to be present on site before or after groups. For inpatient treatment centers, they might want us to visit during meal times to talk with individuals while they are eating and discuss the research study opportunity. A member of the project team (the PI, RA/Project Coordinator, or Co-I) will use the in-person recruitment script (see "in person recruitment script.docx") provide the participant with an iPad to facilitate the informed consent process and research survey. If we do not have enough iPads at any point, we will encourage individuals to complete the survey on their phone or mobile device. We will have paper copies of the survey as back up if needed or preferred by individuals. All paper copies will be stored in a locked cabinet within a locked room that only the PI has access to. All paper copies will be double-entered for quality assurance. A member of the project team will provide the participant with their incentive upon completion of the survey. Tabling to recruit participants may also happen virtually, if preferred by treatment centers. For virtual tabling, a research assistant will attend online group meetings, with permission from the treatment center, to present the opportunity to participate to clients. Treatment center staff will provide the study flyer to clients and interested individuals will be instructed to contact the study email or phone number. Virtually tabling will occur using secure wifi and using a link provided by the treatment center or the research assistant's HIPAA protected zoom account.

For in person recruitment, all safety protocols will be followed in accordance with the University of Oregon's Stage 1 and 2 Research Activities protocol. The Stage 1 and 2 form will be completed and submitted separately.

Participants who complete procedure 2 (the baseline only survey) will be compensated \$50 via check or gift card in the mail, sent electronically or provided in-person if research is conducted in-person. If participants do not have a mailing address, they will have the opportunity to indicate as such and provide a phone number for the project coordinator to follow-up.

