## B. Specific Aims/Study Objectives

Aim 1: Document Baseline Differences Among Opioid Misusing and Non-Opioid Using (other substance using) Fathers and Child Functioning (note, we are recruiting from substance use treatment centers and substance use related pages on social media so some fathers use opioids while others do not just by nature of who attends treatment)

Aim 2: Understand how Opioid Misuse is related to treatment outcomes and whether the intervention shows promise for this population

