## C. Methods, Materials and Analysis

This study will include two procedures; Procedure 1 is for the intervention study and Procedure 2 is for the baseline study.

Procedure 1 for the intervention study is a randomized-control trial of the Fathering Through Change (FTC) intervention. Our goal is to recruit up to 120 participants and randomly assign them to either intervention or control. Treatment centers throughout the state of Oregon will help to facilitate recruitment. They will do outreach to men currently receiving treatment services and to men who have received treatment from the respective treatment centers in the past. Individuals who receive communication from a treatment center may also share that information with their peers in recovery. Those individuals will also be welcome to participate if they meet the inclusion/exclusion criteria. The clinician does not have to be vetted by in order to provide services for men currently receiving treatment since they are not an employee of any treatment center and have been vetted by the University of Oregon. Additionally, the study will recruit participants by advertising on social media websites, specifically Facebook and Reddit. Public account pages will be made on each platform to advertise the current study. The recruitment flyer and posted text (see "Fathering Through Change (FTC) Intervention Research Study.pdf" and "Facebook or reddit example posting.docx" will be posted on both platforms. For Facebook, the flyer and posted text will be posted to groups related to heroin/opioid/substance use recovery and parenting. For Reddit, a similar process will occur, such that the flyer and posted text will be posted to "communities" that relate to heroin/opioid/substance use recovery and parenting in recovery. In addition to the flyer and posted text, contact information will be shared that can connect interested individuals with affiliated research personnel. All individuals expressing interest in the study will be directed to contact the project coordinator to complete the eligibility screener.

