For Procedure 2 interested individuals will text or email "I'm Interested" to the study phone number or email. The project coordinator will complete the eligibility screener and, if eligible to participate, send the eligible individual the link to the Qualtrics survey. If eligible to participate, the survey will continue to inform the eligible individual to review the consent form (see "Informed Consent\_Baseline only\_A6.docx"). Once consent is completed, the participant will complete the baseline survey that includes the same questionnaires from the previously approved baseline survey of the intervention study. Participants will have the opportunity at the end of the Qualtrics survey to indicate if they consent to be re-contacted for future research studies; in effort to potentially enroll them in the intervention study (Procedure 1). Participants will be compensated \$50 for completing the baseline survey.

Procedure 2 will recruit participants through both social media and treatment center outreach. Treatment centers previously contacted for Procedure 1 will be contacted via email (see "email template for treatment centers\_baseline.docx") to send them a flyer (see "Baseline only FTC flyer.pdf"). For social media, we will recruit participants by advertising on social media websites, specifically Facebook and Reddit. Public account pages will be made on each platform to advertise the current study. The recruitment flyer and posted text (see "baseline only FTC flyer.pdf" and social media template\_baseline.docx") will be posted on both platforms. For Facebook, the flyer and posted text will be posted to groups related to heroin/opioid/substance use recovery and parenting. For Reddit, a similar process will occur, such that the flyer and posted text will be posted to "communities" that relate to heroin/opioid/substance use recovery and parenting in recovery.

In effort to reduce fraudulent survey submissions anticipated from posting our study on social media platforms, three actions will be taken: 1) we will remove the compensation option "giftcard by text" and prompt "if receiving mail is a problem for you check this box" followed by the option to indicate, "I don't have a mailing address. Please follow-up with me", 2) implement IP address restrictions on the Qualtrics survey settings, and 3) add three fill in the blank attention checks to assess for fraudulent and bot responses (see "example attention check questions.docx").

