The funding agency required a Data Safety Monitoring Plan for this research at the time of funding proposal. A copy of the DSMP submitted to the funder is attached; however, it should be noted that there are some discrepancies due to the evolution of the project following proposal. The discrepancies are documented in a separate Memo to File. The key differences are that no information is being obtained from the treatment facilities, and the research no longer plans to include families and children as subjects. We are no longer excluding fathers of children with a developmental disability since children are not research subjects. Only fathers will participate. Additionally, our sample size is now 120 instead of 80. There will be three points of data collection rather than two. All other key components of the DSMP as proposed persist including the defined roles and responsibilities, procedures for monitoring site performance, procedures for monitoring data integrity, protecting confidentiality, and safety reporting and monitoring. Additionally, in the event of a crisis such as expressed elevated suicidality or intent to harm self or other, [name], who is currently receiving supervision to obtain licensure, will create a safety plan with the client (attached) and will make a referral to the appropriate agency such as the emergency department, back to the treatment center they are receiving services from if the client is currently receiving services, a local therapy center such as Options Counseling, or Child Welfare if warranted.

There is no established Data and Safety Monitoring Board/Committee (DSMB/C) as noted in the DSMP.

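### Is the opioid versus non-opioid baseline comparison (Aim 1) compromised because the plan does not say whether it uses 79 or 120 fathers, or how differing abstinence windows are handled?

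*Protocol*

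**What the plan says.** Protocol section B states Aim 1 as "Document Baseline Differences Among Opioid Misusing and Non-Opioid Using (other substance using) Fathers and Child Functioning". It gives no procedure and no sample size.

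Protocol section C introduces the two parts of the study with the words "Procedure 1 is for the intervention study and Procedure 2 is for the baseline study". It adds that the Procedure 2 survey "includes the same questionnaires from the previously approved baseline survey of the intervention study". On recruitment it says "Treatment centers previously contacted for Procedure 1 will be contacted via email", and it uses the same two social media platforms for both procedures. The Analysis Plan paragraph in that section lists t-tests, 2 x 2 ANCOVAs, MANOVAs and path models for the aims together, without matching a method, sample or covariate to either aim.

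Protocol section D limits abstinence to at least 1 day and under 18 months for Procedure 1, and at least 1 day and under 36 months for Procedure 2. It sets a ceiling of 120 for the baseline survey, and says of that figure "This number includes the participants who also participated in procedure 1". With 41 fathers already enrolled in Procedure 1, "we expect that no more than 79 participants will be recruited for the baseline only survey".

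Protocol section G says "our sample size is now 120 instead of 80".

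The SAP covers the models for the 6-week and 4-month follow-ups, the false discovery rate correction and missing data. It does not mention Aim 1.

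**The concern.** Aim 1 is one of only two stated aims, so one expects to be told who is analysed. Someone who takes the section C label literally could analyse Procedure 2 alone, while someone who follows the section D count would pool both procedures. The two choices describe somewhat different populations, with different precision, and an unstated set could in principle be picked after the results are seen.

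Pooling raises a second question. Procedure 2 admits fathers with up to twice the abstinence and may reach men on site, including at inpatient centers and a methadone clinic. Procedure 1 tells treatment centers not to message current inpatients. If the opioid share differs between procedures, and outcome levels do too, the crude opioid contrast would carry some of the difference between procedures. No adjustment, restriction or sensitivity analysis is written down.

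**Working it through.** **1. The plan's own figure.** Section D defines new Procedure 2 recruitment as the ceiling less the number in Procedure 1: 120 − 41 = 79. This reproduces exactly. It also shows what 79 is: the most fathers still to be recruited within a baseline total of 120.

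**2. The two readings side by side.**
- *For 79:* the section C label "Procedure 1 is for the intervention study and Procedure 2 is for the baseline study". It names a procedure and does not define an analysis set. Aim 1 itself does not mention Procedure 2.
- *For 120:* the ceiling expressly counts the Procedure 1 fathers, and both procedures use the same baseline questionnaires.
- *Not decisive:* the 120 in section G fits pooling, but section C also says "Our goal is to recruit up to 120 participants and randomly assign them to either intervention or control", so that number is used for more than one thing. The clash between that sentence and the section D cap of 80 concerns the size of Procedure 1 and does not bear on Aim 1.

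The weight of the text is with pooling.

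**3. What the choice costs in precision.** The documents give no alpha, power or opioid share for Aim 1. I assume two-sided 5%, within-group SD 1, and an opioid share of 50% or 70%. Half-width = t(0.975, N−2) × √(1/a + 1/b), with a and b the group sizes. The detectable difference at 80% power comes from the noncentral t distribution.

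| N | a / b | t × √(1/a + 1/b) | Half-width (SD) | Detectable (SD) |
|---|---|---|---|---|
| 120 | 60 / 60 | 1.980 × 0.1826 | 0.36 | 0.52 |
| 120 | 84 / 36 | 1.980 × 0.1992 | 0.39 | 0.56 |
| 79 | 40 / 39 | 1.991 × 0.2250 | 0.45 | 0.64 |
| 79 | 55 / 24 | 1.991 × 0.2446 | 0.49 | 0.69 |

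The width ratio at an even split is 0.448 / 0.362 = 1.24. Both totals are ceilings, so achieved precision may be lower on either reading.

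**4. What pooling could do to the crude contrast.** Suppose there is no true opioid difference and outcomes are shifted by s SD in Procedure 2. The spurious difference is then s × (share of opioid fathers who come from Procedure 2 − share of non-opioid fathers who do).
- *Opioid share 50% in Procedure 1, 70% in Procedure 2:* 20 and 55 opioid fathers, 21 and 24 non-opioid. 55/75 − 24/45 = 0.733 − 0.533 = 0.20. This gives 0.04 SD at s = 0.2 and 0.10 SD at s = 0.5.
- *40% and 70%:* 16 and 55 opioid, 25 and 24 non-opioid. 55/71 − 24/49 = 0.775 − 0.490 = 0.285. This gives 0.06 SD at s = 0.2 and 0.14 SD at s = 0.5.
- *Equal shares:* essentially zero for any s.

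Each of these is below the half-width of 0.36 to 0.39 SD that 120 fathers allow. The shares and shifts are all assumptions, because the documents supply neither.

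**5. Whether the two samples can be combined.** The Procedure 1 window lies wholly inside the Procedure 2 window, so every Procedure 1 father meets the Procedure 2 abstinence criterion. The child-age, contact, language and adult-age criteria are the same, as is the stated priority for fathers who have misused opioids. Pooling breaks no eligibility rule.

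**The case for a change.** The best case for a change is that it is cheap. One sentence would name the set, and one more would put a procedure-adjusted estimate beside the crude one. With procedure as a covariate, about 96% of the information on the opioid contrast is kept at opioid shares of 50% and 70%, and about 91% at 40% and 70%. A descriptive estimate still needs a named population, and the analysis sections are present and silent, so the omission is not a product of redaction. Procedure 2 fathers may also agree to be re-contacted for possible entry to Procedure 1, so a pooled file must count each man once.

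The silence does stand as a fact, and a report of Aim 1 should say who was included. The rest is weaker:
- For an aim that sets out to document differences, the crude pooled difference is a legitimate target, and the mix of recruitment is part of what it describes. Calling it biased presupposes a procedure-adjusted target.
- The listed ANCOVAs already leave room for a covariate if the analyst wants one.
- Double counting is largely moot, because section D treats Procedure 1 recruitment as finished and counts its fathers within the 120.
- The SAP is written in the past tense. If Aim 1 has already been analysed, naming the set now would not restore prespecification.

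**Conclusion.** No change to the plan follows. This is a detail left unsaid, and no stated rule produces a wrong result. A sensible analyst would fill it by pooling the two nested samples and comparing the opioid groups with the t-tests or ANCOVAs the Protocol lists. The alternative reading rests on one label and would cost about 24% in interval width under an even opioid split.

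The possible distortion from pooling is unknown and may be zero. It reaches 0.04 to 0.06 SD at an assumed 0.2 SD shift between procedures, and 0.10 to 0.14 SD only if a 0.5 SD shift is combined with a gap of 20 to 30 percentage points in opioid share. Nothing in the documents points to either condition, and the shared recruitment channels and shared opioid priority give no particular reason to expect them. An adjusted estimate, or one restricted to fathers under 18 months abstinent, would be a reasonable extra but is a matter of preference, with no gain that can be shown from the documents. The randomised comparison and the SAP's outcome models are unaffected.
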